14.1 Primary Endpoint: Best Overall Response and Objective Response

Objective Response (OR) is defined as a confirmed Best Overall Response (BOR) of complete response (CR) or partial response (PR). Requirements for confirmation of responses is detailed below.

BOR will be based on investigator-reported overall responses from the treatment start date until documented disease progression, assessed in accordance to RECIST v1.1 (Eisenhauer et. al.). Only tumor assessments performed before the start of subsequent anti-cancer treatments will be considered in the assessment of BOR. If a tumor assessment was performed on the same day as start of new anti-cancer treatment, it will be assumed that the tumor assessment was performed prior to the start of the new anti-cancer treatment and will be included in the evaluation of BOR. Clinical deterioration will not be considered as documented disease progression, for the sake of BOR evaluation.

Confirmed BOR requires the following:

- Complete response (CR): at least two determinations of CR at least 4 weeks apart (with no PD in between)
- Partial response (PR): at least two determinations of PR or better (PR followed by PR or PR followed by CR) at least 4 weeks apart (and not qualifying for a CR), with no PD in between
- Stable disease (SD) (applicable only to participant with measurable disease at baseline): at least one SD assessment (or better) at least 6 weeks after treatment start date (and not qualifying for CR or PR).
- Non-CR/non-PD (applicable only to participants with non-measurable disease at baseline): at least one non-CR/non-PD assessment (or better) at least 6 weeks after treatment start date (and not qualifying for CR or PR).
- Progressive disease (PD): PD ≤12 weeks after treatment start date (and not qualifying for CR, PR, non-CR/non-PD or SD).
- Not Evaluable (NE): all other cases.

SD can follow PR only in the rare case that tumor increases by less than 20% from the nadir, but enough that a previously documented 30% decrease from baseline no longer holds. If this occurs the sequence PR-SD-PR is considered a confirmed PR. A sequence of PR – SD – SD – PD would be a best response of SD if the minimum duration for SD definition has been met.

Participants who do not have an on-treatment radiographic tumor assessment due to early progression, who receive anti-tumor treatments other than the study treatments prior to reaching confirmed CR or PR, or who die, progress, or drop out for any reason prior to reaching confirmed CR or PR will be counted as non-responders in the assessment of OR.

Each participant will have an objective response status (0: 'no OR'; 1: 'OR'). The confirmed Objective Response Rate (ORR) will be calculated along with the two-sided 95% CI using the Clopper-Pearson method (exact CI for a binomial proportion as computed by default by the SAS FREQ procedure using the EXACT option).

Disease Control (DC) is defined as a confirmed BOR of CR, PR, SD or Non-CR/non-PD. DC rate (DCR) is the proportion of participants with DC. DCR will be calculated along with the two-sided 95% CI using the Clopper-Pearson method.

In addition, the frequency (number and percentage) of participants with confirmed BOR of CR, PR, SD, PD, non-CR/non-PD, and NE will be tabulated. Participants with BOR of NE will be summarized by reason for having NE status. The following reasons will be used in hierarchical order:

- No baseline assessment
- No post-baseline assessments due to death before first post-baseline assessment
- No post-baseline assessments due to other reasons
- All post-baseline assessments have overall response NE
- Subsequent anticancer therapy started before first post-baseline assessment
- SD of insufficient duration (<6 weeks after start date)
- PD too late (>12 weeks after start date of treatment)

Special and rare cases where confirmed BOR is NE due to both early SD and late PD will be classified as 'SD too early'.

Participant lesion measurements, tumor assessments, and best overall response, will be included in a listing.

14.2 Duration of Response

Given the small number of subjects and the low likelihood that any will experience an objective response, duration of response will not be analyzed.

14.3 Overall Survival

Overall survival (OS) is defined as the time from treatment start to the date of death due to any cause. OS for participants without death prior to cut-off will be censored at date of last contact. Overall survival in months is calculated as follows:

OS (months) = [date of death or censoring—treatment start date +1]/30.4375

The OS time or censoring time will also be presented in a participant listing.

14.4 Progression-Free Survival

Progression Free Survival (PFS) time is defined as the time from start date to the date of the first documentation of objective progression of disease (PD) or death due to any cause, whichever

occurs first. The tumor response will be determined according to RECIST 1.1 (Eisenhauer et. al.) and assessed by the investigator. PFS censoring logic is equivalent to DR censoring.

PFS time (in months) = (Date of PD or death – treatment start date + 1)/ 30.4375 (months)

Kaplan-Meier estimates (product-limit estimates) will be presented with a summary of associated statistics including the median OS time with two-sided 95% CIs. The CIs for the median will be calculated according to Brookmeyer and Crowley. The estimate of the standard error will be computed using Greenwood's formula.

Unique reasons for censoring will be summarized based on assignment to the categories in Table 3, following the hierarchy shown.

Table 3 PFS Censoring Reasons and Hierarchy

Hierarchy	Condition	Censoring Reason
1	No adequate baseline assessment	No baseline assessment
2	No death within 12 weeks of treatment start and no adequate post-baseline tumor assessment, including if death is observed > 12 weeks after treatment start	No post-baseline tumor assessment
3	Start of subsequent anti-cancer therapy before event, including if no event was observed	Start of subsequent anti-cancer therapy
4	Event more than 2*(scheduled time between tumor assessments) a weeks after last adequate post-baseline tumor assessment	Event after 2 or more missing assessments
5	No event and end of study reason is "Withdrew consent"	Withdrawal of consent
6	No event and "Lost to follow-up" indicated on any disposition eCRF page	Lost to follow-up: Status collected on eCRF page
7	Censoring date > 2*(scheduled time between tumor assessments) weeks before cut-off date	Lost to follow-up: two or more missing scans preceding data cut date
8	No event and none of the conditions in the above hierarchy are met	Administrative censoring: Ongoing in the study without an event

^a Per protocol, subjects are to receive tumor scans once every six weeks for the first six cycles (18 weeks), then every 9 weeks thereafter.

The PFS time/censoring time and the reasons for censoring will also be presented in a participant listing.

15 Safety Analyses

Analysis Set: FAS/SAF

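### Part C PFS, Table 3 row 4: a progression first seen after both opening scans were missed stays an event, while a death after the same gap is censored

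*SAP*

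**What the plan says.** All references are to the Part C Integrated Analysis Plan.

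- **Event (section 14.4).** PFS runs to "the date of the first documentation of objective progression of disease (PD) or death due to any cause, whichever" comes first.
- **Table 3, row 2.** The participant is censored for having no post-baseline tumor assessment under the condition "No death within 12 weeks of treatment start and no adequate post-baseline tumor assessment, including if death is observed > 12 weeks after treatment start".
- **Table 3, row 4.** The condition is "Event more than 2*(scheduled time between tumor assessments) a weeks after last adequate post-baseline tumor assessment". The lone letter is the pointer to footnote a. The reason attached to this row is "Event after 2 or more missing assessments".
- **Footnote a.** Under the protocol, "subjects are to receive tumor scans once every six weeks for the first six cycles (18 weeks), then every 9 weeks thereafter". The first scans are therefore due at weeks 6, 12 and 18, and the next at week 27.
- **Source of the rule.** Section 14.4 also says that "PFS censoring logic is equivalent to DR censoring". Section 14.2 states that duration of response will not be analysed and gives no censoring rule.

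Section 14.4 plans Kaplan-Meier estimates with a median and lists PFS times and censoring reasons by participant. Section 6 reports that Part C stopped after 13 participants.

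**The concern.** Row 4 is meant to remove events whose timing is unreliable because scans were missed. It counts only from an earlier post-baseline scan, so it does not reach the participant who missed scans from the very start. That participant's progression could have occurred at any time since treatment began, but it is dated at the first scan that happened to be done. Row 2 already guards against the same situation for deaths, counting from treatment start.

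At stake is whether a progression and a death with the same assessment history are handled alike, and whether two missed scans at the start are handled like two missed scans later. In a group of 13, one participant handled differently is visible in the curve.

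**Working it through.** The plan states no figure to reproduce. The check applies Table 3 in hierarchy order to specific histories, each with an adequate baseline and no subsequent therapy.

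**Inputs.** Scans are due at weeks 6, 12, 18, 27 and 36 (footnote a). The row 4 limit is 2 × 6 = 12 weeks in the six-weekly period and 2 × 9 = 18 weeks afterwards. The row 2 limit for deaths is 12 weeks from treatment start, which equals 2 × 6.

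| History | Rows 1–3 | Row 4 | Result as written |
|---|---|---|---|
| A. Weeks 6 and 12 missed, first scan at week 18 shows PD | none applies: baseline adequate, a post-baseline scan exists, no new therapy | no earlier post-baseline scan to count from | event at week 18 |
| B. Death at week 18, no post-baseline scan | row 2 applies | not reached | censored |
| C. Scan at week 6, weeks 12 and 18 missed, PD at week 27 | none applies | 27 − 6 = 21, above both 12 and 18 | censored |
| D. Death at week 10, no scan | row 2 does not apply (10 is within 12) | nothing to count from | event |
| E. Week 6 missed, PD at week 12 | none applies | nothing to count from | event |

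For A, rows 5, 6 and 8 require that there be no event, and row 7 needs a censoring date, which an event does not have. Nothing later in the table catches it. The recorded PFS is (126 + 1)/30.4375 = 4.17 months. PD first seen at week 13, 27 or 36 with no earlier scan is also an event, while a death in the same week with no scan is censored.

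**With the gap counted from treatment start when no earlier post-baseline scan exists:**
- A: 18 − 0 = 18 > 12, so censored, like B and C.
- First-scan PD at week 13 (13 > 12), week 27 (27 > 18) or week 36 (36 > 18): censored.
- D: 10 is below 12, so still an event. E: 12 does not exceed 12, so still an event.

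**Size.** One such participant is 1/13 = 7.7% of Part C. Section 14.4 states no censoring date, so the two invented data sets below assume censoring at Day 1. Each has 12 other participants, all with events.

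1. Others: 5 events at week 6, 3 at week 12, 2 at week 18, 1 at week 27, 1 at week 36.
   - Case A counted at week 18: S(12) = 5/13 = 0.385, S(18) = 2/13 = 0.154, median 12 weeks.
   - Case A censored at Day 1: S(12) = 4/12 = 0.333, S(18) = 2/12 = 0.167, median 12 weeks.
2. Others: 6 events at week 6, 3 at week 18, 3 at week 27.
   - Case A counted: S(6) = 7/13 = 0.538, median 18 weeks, S(18) = 3/13 = 0.231.
   - Case A censored: S(6) = 6/12 = 0.500 exactly, median 12 weeks by the midpoint convention, S(18) = 3/12 = 0.250.

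The median does not move in the first set. It moves in the second only because the curve sits exactly at 0.5.

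**The case against.** **Table 3 only classifies reasons.** Section 14.4 introduces it as a way to summarise why participants were censored and refers to duration-of-response censoring for the logic. That is fair as a description, but section 14.2 contains no such rule, so Table 3 is the only operative text. A programmer could read treatment start into row 4, but that overrides the word post-baseline.

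**Keeping a known progression has merit.** Censoring it discards an observed event and raises the curve afterwards (0.154 to 0.167 and 0.231 to 0.250 above). This is true. It is also the choice the plan already makes for gaps later in follow-up, so extending it is not a new trade-off.

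**Stronger readings the documents do not support:**
- *Progressions and deaths follow different rules throughout PFS.* They do not. Row 4 refers to events of either kind and treats them alike whenever an earlier post-baseline scan exists.
- *Row 4 never censors a progression*, because the PD scan is itself the last adequate assessment. This makes the row empty for progressions and defeats its evident purpose.
- *PFS contradicts best overall response*, because section 14.1 gives the same late first PD the not-evaluable reason "PD too late (>12 weeks after start date of treatment"). Best response classifies within a window and PFS dates an event, so the two may legitimately differ.
- *PD at week 24 after a week 6 scan shows the inconsistency.* Week 24 is not a scheduled scan. Its 18-week gap exceeds 12 but not 18, and Table 3 does not say which interval applies. Week 27 is the comparison that holds under both.

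**Small consequence.** PFS is secondary and descriptive in a terminated part of the study, and each participant's time and censoring reason are listed. This stands and sets the priority.

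**Conclusion.** The point holds in a narrow form. As written, row 4 misses an event that its own label describes: a progression after week 12 with no earlier post-baseline scan. A death with the same history is censored by row 2, and a progression after two scans missed later is censored by row 4. No other text in the plan closes the gap.

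The effect is zero if nobody missed both opening scans. Otherwise each case is 1 of 13 participants (7.7%). A reader might infer that the reported median is materially wrong, but the documents do not support that. The illustrations rest on invented event times and an assumed Day 1 censoring date, and they show that one case may or may not move the median. Priority: minor.

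**What to change.** Reword row 4 so that it covers an event falling more than two scheduled scan intervals after the latest adequate tumor assessment that precedes it or, where no adequate post-baseline assessment precedes it, after treatment start. State in section 14.4 the censoring date used for such cases. If the sponsor means a late first-scan progression to count as an event, the plan should say so instead.

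The cost is one line of text and a small programming change. The statistical downside is that a rare known progression becomes a censored observation, so there may be one event fewer and slightly higher PFS estimates after that time. The rule works on elapsed time, so a first scan done shortly after week 12 would also be caught, as row 2 already does for a death at that point.

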15.1 Primary Endpoint: Adverse Events

Treatment-emergent adverse events (TEAE) are those events with onset dates occurring within the on-treatment periods as defined in Section 9.10.

Adverse events related to study treatment are those events with relationship missing, unknown or yes.

Serious adverse events (SAEs) are AEs with the eCRF field "Serious adverse event" marked "Yes"

AEs leading to temporary treatment discontinuation are those with the action "Drug interrupted" selected.

AEs leading to permanent treatment discontinuation are those with "Drug withdrawn" checked as an "Action taken with M4344" on the Adverse Events eCRF page.

AEs leading to death are AEs with NCI-CTCAE toxicity Grade 5 or outcome "fatal".

All analyses described in Section 15.1 will be based on TEAEs if not otherwise specified. Separate listings will be produced for AEs outside the on-treatment period and AEs attributed to the impact of COVID-19.

Unless otherwise specified, TEAEs will be summarized by number and percentage of participants with the TEAE in the category of interest, by primary SOC, in alphabetic order, and PT in decreasing frequency for the Total column.

Each participant will be counted only once within each SOC or PT. If a participant experiences more than one AE within a given SOC or PT, only the AE with the strongest relationship or the worst severity, as appropriate, will be included in the summaries of relationship and severity.

Adverse events will be summarized by worst severity (according to NCI-CTCAE version 5.0) per participant, using the latest version of MedDRA preferred term (PT) as event category and MedDRA primary system organ class (SOC) body term as Body System category.

In case a participant has events with missing and non-missing grades, the maximum of the non-missing grades will be displayed. No imputation of missing grades will be performed.

Incomplete AE-related dates will be handled as specified in Section 9.12.2.

The following tables will be created:

- The overall summary of AEs table will include the frequency (number and percentage) of participants with each of the following:
 - TEAEs
 - TEAEs with NCI-CTCAE Grade ≥ 3, by grade
 - Related TEAEs
 - Related TEAEs with NCI-CTCAE Grade ≥ 3, by grade

- TEAEs leading to temporary treatment discontinuation
- Related TEAEs leading to temporary treatment discontinuation
- TEAEs leading to permanent treatment discontinuation
- Related TEAEs leading to permanent treatment discontinuation
- Serious TEAEs
- Non-Serious TEAEs
- Related Serious TEAEs
- TEAEs leading to death
- Related TEAEs leading to death
- TEAEs by SOC, PT and worst CTCAE toxicity grade
- Treatment related TEAEs by SOC, PT and worst CTCAE toxicity grade
- TEAEs leading to permanent discontinuation of M4344 by SOC and PT
- Related TEAEs leading to permanent discontinuation of M4344 by SOC and PT

Clinical trial.gov and EudraCT -requirements

Summary tables for non-serious adverse events excluding SAEs will be provided. The non-serious AEs are not restricted to non-serious TEAEs.

15.2 Deaths, Other Serious Adverse Events, and Other Significant Adverse Events

15.2.1 Deaths

All deaths, deaths within 30 days after last dose of study treatment, deaths within 60 days after first dose, as well as reason for death, will be tabulated based on information from the "Death" eCRFs page.

- Number of deaths
- Number of deaths within 30 days after last dose of study treatment
- Number of deaths within 60 days after first dose of study treatment
- Primary Reason of Death
 - Disease progression
 - Event related to study treatment
 - Event not related to study treatment
 - Subset of subjects who died due to the impact of COVID-19
 - Unknown

In addition, date and cause of death will be provided in individual participant data listing together with selected dosing information (date of first / last administration, number of cycles treated).

This listing will include:

- AEs with fatal outcome (list preferred terms of AEs with outcome=fatal)
- Flag for death within 30 days of last study treatment
- Flag for death within 60 days of first study treatment

15.2.2 Serious Adverse Events

The following overall frequency tables will be prepared for serious adverse events (SAEs):

- Incidence of serious AEs by SOC and PT
- Incidence of related serious AEs by SOC and PT

The listings of SAEs will also be provided with the relevant information with a flag for SAEs with onset outside of the on-treatment period.

15.3 Primary Endpoint: Clinical Laboratory Evaluation

Parameters with NCI-CTCAE grades available:

Laboratory results will be classified according to the NCI-CTCAE criteria version 5.0. Some of the toxicity gradings are based on laboratory measurements in conjunction with clinical findings. Non-numerical qualifiers (with the exception of fasting flags) will not be taken into consideration in the derivation of CTCAE criteria. For example, hypokalemia Grade 1 and Grade 2 are only distinguished by a non-numerical qualifier (symptomatic and intervention indicated) and therefore Grade 2 will not be derived. Abnormalities classified according to NCI-CTCAE toxicity grading version will be described using the worst on-treatment grade. For those parameters which are graded with two directions of toxicities such as potassium (hypokalemia/hyperkalemia), the toxicities will be summarized separately. Low direction toxicity (e.g., hypokalemia) grades will be set to 0 when the variables are derived for summarizing high direction toxicity (e.g., hyperkalemia), and vice versa.

The laboratory toxicities will be tabulated with counts of participants and percentages during the on-treatment period. The denominator to calculate percentages for each laboratory parameter is the number of participants in the analysis population. Subjects without an on-treatment result or results which are not CTCAE gradable will be counted in the "Missing" category.

- The summary of laboratory parameters by CTCAE grade table will include number and percentage of participants with Grade 1, 2, 3, 4, 3/4, and any grade (1 to 4), laboratory abnormalities during the on-treatment period.
- The shift table will summarize baseline CTCAE grade versus the worst on-treatment CTCAE grade. The highest CTCAE grade during the on-treatment period is considered as the worst grade for the summary.

The following parameters are CTCAE-gradable:

Hematology:

Hemoglobin, leukocytes, lymphocytes, neutrophils/absolute neutrophil count, platelet count.

Serum Chemistry:

Albumin, alkaline phosphatase, alanine aminotransferase (ALT), amylase, aspartate aminotransferase (AST), total bilirubin, cholesterol, creatinine, creatine kinase, potassium, sodium, magnesium, calcium, glucose, gamma glutamyl transferase (GGT), lipase, phosphates, triglycerides.

Please see the further details of NCI-CTCAE gradable parameters in the Appendix.

For calcium, CTCAE grading is based on Corrected Calcium. Corrected Calcium is calculated from Albumin and Calcium as follows

Corrected calcium (mmol/L) = measured total Calcium (mmol/L) + 0.02 (40 - serum albumin [g/L])

Liver function tests: Alanine aminotransferase (ALT), aspartate aminotransferase (AST), and total bilirubin are used to assess possible drug induced liver toxicity. The ratios of test result over upper limit of normal (ULN) will be calculated and classified for these three parameters during the on-treatment period.

Summary of liver function tests will include the following categories. The number and percentage of participants with each of the following during the on-treatment period will be summarized by treatment group:

- ALT ≥ 3×ULN, ALT ≥ 5×ULN, ALT ≥ 10×ULN, ALT ≥ 20×ULN
- AST ≥ 3×ULN, AST ≥ 5xULN, AST ≥ 10×ULN, AST ≥ 20×ULN
- (ALT or AST) ≥ 3×ULN, (ALT or AST) ≥ 5×ULN, (ALT or AST) ≥ 10×ULN, (ALT or AST) ≥ 20×ULN
- TBILI ≥ 2×ULN
- Concurrent ALT ≥ 3×ULN and TBILI ≥ 2×ULN
- Concurrent AST ≥ 3×ULN and TBILI ≥ 2×ULN
- Concurrent (ALT or AST) ≥ 3×ULN and TBILI ≥ 2×ULN
- Concurrent (ALT or AST) ≥ 3×ULN and TBILI ≥ 2×ULN and ALP > 2×ULN
- Concurrent (ALT or AST) ≥ 3×ULN and TBILI ≥ 2×ULN and ALP ≤ 2×ULN or missing

Concurrent measurements are those occurring on the same date.

Categories will be cumulative, i.e., a participant with an elevation of AST ≥10×ULN will also appear in the categories \geq 5×ULN and \geq 3×ULN. Liver function elevation and possible Hy's Law cases will be summarized using frequency and percentage.

Parameters with NCI-CTCAE grades not available:

Laboratory results that are not part of NCI-CTCAE will be presented according to categories based on comparison to normal reference ranges (i.e. Low, Normal, and High).

Hematology and chemistry evaluations which cannot be graded per CTCAE criteria will be summarized as frequency (number and row percentage) of participants with:

- shifts from baseline normal to at least one result above normal during on-treatment period
- shifts from baseline normal to at least one result below normal during on-treatment period

In this study, these apply to the following parameters:

Hematology:

Hematocrit, Red Blood Cell (RBC), Reticulocytes, Mean Corpuscular Hemoglobin (MCH), Mean Corpuscular Volume (MCV), Mean Corpuscular Hemoglobin Concentration (MCHC).

Serum Chemistry:

Chlorine, C-Reactive Protein, Lactate Dehydrogenase (LDH), Total Protein, Total Urea, Uric Acid.

The following figures will be provided:

- An evaluation of Drug-Induced Serious Hepatotoxicity (eDISH) plot will also be created, with different symbols for the different biomarker cohorts, by graphically displaying peak serum ALT(/ULN) vs peak total bilirubin (/ULN) including reference lines at ALT =3×ULN and total bilirubin =2×ULN.
- An equivalent eDISH plot of peak serum AST (/ULN) vs peak total bilirubin (/ULN) will also be provided.

Listings of laboratory results will be provided for all hematology and biochemistry parameters. The listings will be sorted by parameter and visit for each participant. Laboratory values that are outside the normal range will be flagged in the data listings, and corresponding normal ranges and CTCAE grades will be provided.

In addition, a listing of all TBILI, ALT, AST and ALP values for participants with at least one post-baseline TBILI $\geq 2 \times ULN$, ALT $\geq 3 \times ULN$ or AST $\geq 3 \times ULN$ will be provided.

Any other laboratory parameter collected will be listed in dedicated listings presenting all relevant information collected on the eCRF or by the central lab:

Coagulation: [activated partial thromboplastin time (aPTT) and prothrombin time (INR).

- Urinalysis: all urinalysis parameters
- Other parameters: hormone, and immunology parameters
- Pregnancy test

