9.10 Definition of On-treatment Period

The on-treatment period is defined as the time from the first dose of study treatment day to the last administration day of study treatment + 30 days, the data cutoff day, or death, whichever occurs first.

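### Part C counts possible Hy's Law cases on same-date values only, so the table can undercount sequential or split-date cases, and nothing links it to the eDISH plots

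*SAP*

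**What the plan says.** The SAP file holds two plans; this point concerns the Part C plan, section 15.3, on liver function tests.

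- **Table.** Five rows combine a transaminase limit with a bilirubin limit: ALT alone, AST alone, either one, and either one split by ALP. The central row is "Concurrent (ALT or AST) ≥ 3×ULN and TBILI ≥ 2×ULN". The rule for all five is "Concurrent measurements are those occurring on the same date". The section then says: "Liver function elevation and possible Hy's Law cases will be summarized using frequency and percentage". It gives no other definition of a possible Hy's Law case and no time window.
- **Plots.** The eDISH figure is built by "graphically displaying peak serum ALT(/ULN) vs peak total bilirubin (/ULN) including reference lines at ALT =3×ULN and total bilirubin =2×ULN". For AST: "An equivalent eDISH plot of peak serum AST (/ULN) vs peak total bilirubin (/ULN) will also be provided". Neither requires the two peaks to share a date.
- **Listing.** The plan adds: "In addition, a listing of all TBILI, ALT, AST and ALP values for participants with at least one post-baseline TBILI" at or above 2×ULN, or ALT or AST at or above 3×ULN.
- **Period.** The table covers the on-treatment period, which section 9.10 runs from first dose "to the last administration day of study treatment + 30 days, the data cutoff day, or death, whichever occurs first".

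**The concern.** The table and the plots use the same two cut-offs but different timing rules. If bilirubin rises as transaminases are already falling, there may be no single date on which both limits are exceeded. The combined rows then omit the participant while the plot shows them in the upper-right quadrant. The same happens if the two tests come from samples taken on different days.

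Laboratory abnormalities belong to the primary safety endpoint of Part C (section 5), and section 15.3 says these tests serve to assess possible liver toxicity of the drug. A summary row reading zero is the figure most likely to be carried into report text. The rows also treat incomplete panels unevenly. A missing ALP still leaves the participant counted, because the last row groups it with ALP ≤ 2×ULN. A bilirubin value missing on the date of the transaminase rise leaves the participant uncounted unless another date qualifies.

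**Working it through.** The plan states no figure to reproduce here, so the check applies its rules to example profiles.

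**Rules**

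- Same-date row: some date d has ALT(d) ≥ 3×ULN and TBILI(d) ≥ 2×ULN.
- eDISH upper right: max ALT ≥ 3×ULN and max TBILI ≥ 2×ULN, on any dates.
- Listing: any TBILI ≥ 2×ULN, or any ALT or AST ≥ 3×ULN.
- Added window row, for illustration: TBILI ≥ 2×ULN from 0 to w days after a date with ALT ≥ 3×ULN, with w = 14 or 30. These lengths are assumptions and do not come from the documents.

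**Profiles** (assumed, in multiples of ULN; AST taken as below 3×ULN throughout and all dates as on-treatment)

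| Profile | Values | Same-date row | eDISH upper right | Window, 14 or 30 days | Listing |
|---|---|---|---|---|---|
| A: rises overlap | day 8 ALT 8, TBILI 1.0; day 15 ALT 5, TBILI 2.5; day 22 ALT 2, TBILI 2.2 | yes | yes | yes | yes |
| B: sequential | day 8 ALT 6, TBILI 1.0; day 15 ALT 2.8, TBILI 2.3 | no | yes | yes | yes |
| C: split dates | day 8 ALT 6; day 9 TBILI 2.4 | no | yes | yes | yes |
| D: distant peaks | day 8 ALT 4, TBILI 0.8; day 120 ALT 1.0, TBILI 3.0 | no | yes | no | yes |

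Profile A shows that a bilirubin rise after the ALT peak is still counted when ALT remains ≥ 3×ULN on the later date (5 ≥ 3 and 2.5 ≥ 2 on day 15). Profile B fails because ALT is 2.8 < 3 on the only date with TBILI ≥ 2. Profile C fails because no date has both values. Profile D shows the opposite weakness: the peak rule includes two rises 120 − 8 = 112 days apart, which may be unrelated.

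**Size.** The Part C plan, section 6, gives 13 enrolled. Taking all 13 as dosed, so that all are in the FAS/SAF, one reclassified participant moves the count from 0/13 to 1/13 = 7.7%. The plan specifies only counts and percentages for these rows. Exact (Clopper-Pearson) 95% limits are added here to show the scale:

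- 0/13: upper limit = 1 − 0.025^(1/13) = 24.7%.
- 1/13: 0.2% to 36.0%.

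**The case against.** The case against is substantial, and most of it stands.

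- **The case stays visible.** Profile B is counted in the rows for ALT ≥ 3×ULN, ALT ≥ 5×ULN and TBILI ≥ 2×ULN, appears on the ALT eDISH plot, and is in the listing with all its values. With 13 participants, reading that listing is little work. A reader might infer that such a case disappears from the report; the documents do not support that.
- **The two outputs are labelled measures.** One is called concurrent, with the term defined; the other is peak against peak. A reader might infer that they contradict each other. They do not: the first is strict and the second is sensitive, and profile D shows that the plot is not the correct count either.
- **A later bilirubin rise is not always missed.** Profile A is counted.
- **Split draws are hypothetical.** Section 15.3 lists ALT, AST, ALP and total bilirubin together under serum chemistry, and nothing says they are drawn on different days.
- **Any window length is a convention.** The 30 days in section 9.10 is the tail of the on-treatment period, not an interval between transaminase and bilirubin rises.
- **No test or decision rule depends on these rows.** The separate plan for Parts A, A2 and B1 does name bilirubin and ALT/AST increases as special adverse event categories (section 15.3.3), but it gives no reason and lists nausea and vomiting beside them. Reading this as an established liver risk of the drug would be inference.

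What remains is narrower. The only stated count of possible Hy's Law cases uses the strict rule, it can read zero while the plot in the same section shows an upper-right participant, and the plan does not say how the difference will be explained.

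**Conclusion.** The point holds as a possible undercount in the table, of minor severity. The same-date rows can omit a participant whose bilirubin reaches 2×ULN only once transaminases are below 3×ULN, or whose samples fall on different dates. The eDISH plots and the listing retain that participant, but no rule connects them to the count.

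One such participant would make the difference between 0/13 and 1/13 (7.7%). That size assumes all 13 enrolled participants were dosed and that such a case occurs; the documents give no basis for estimating how likely it is. The profiles are illustrations, not trial data.

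**What to change.** In the Part C plan, section 15.3:

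1. Keep the five same-date rows unchanged.
2. Add one row for TBILI ≥ 2×ULN on the same date as, or within a pre-stated number of days after, ALT or AST ≥ 3×ULN. The length is an analysis convention for the sponsor to set, for example 14 or 30 days. Either would capture profiles B and C and leave out D.
3. State that each participant in the upper-right quadrant of either eDISH plot who is absent from the same-date rows will be footnoted with the time gap between the two rises.

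The cost is a few lines of plan text and a small programming change, using values already planned for the listing. The downside is that a participant with two unrelated rises close together may occasionally enter the added row and need a footnote.
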